1. BACKGROUND AND RATIONALE

Belantamab mafodotin - blmf (BLENREP) is a first-in-class anti-B-cell maturation antigen (BCMA) antibody-drug conjugate (ADC) that recently gained regulatory approval for the treatment of relapsed and/or refractory multiple myeloma (RRMM). As the first BCMA-targeted therapy to receive approval for multiple myeloma with an “off-the-shelf” outpatient administration, BLENREP addresses a significant unmet need in RRMM that is refractory to immunomodulatory drugs (IMiD), proteasome inhibitors (PI), and anti-CD38 mAb therapy, otherwise known as triple-class refractory myeloma. However, BLENREP is associated with frequent corneal ocular adverse events, which represents a unique toxicity in multiple myeloma therapeutics. Due to the potential of ocular adverse events, the administration of BLENREP requires a multidisciplinary approach with oncologists and eye care specialists to safely and effectively manage patients on the therapy.

2. OBJECTIVES

This study aims to describe the real-world use of BLENREP and associated patterns of care, including dosing and dose modification, and eye care specialist visits, and associated healthcare utilization and clinical outcomes in patients with relapsed and/or refractory multiple myeloma (RRMM) seen in the Duke Cancer Institute (DCI) clinics.

2.1. Primary Objectives

- Describe the demographic and clinical characteristics of RRMM patients who receive BLENREP treatment at the DCI clinics.
- Describe the treatment characteristics of BLENREP therapy (e.g. dose, length of treatment, delays and dose reductions, reasons for discontinuation) in these patients.
- Describe the clinical outcomes of RRMM patients who receive BLENREP treatment at the DCI clinics, as available.

2.2. Secondary Objectives

[figure not shown]
- Describe Ophthalmology visit patterns before and during treatment, investigating the specific adverse event of interest (keratopathy) as available.
- Explore the magnitude and sources of distress for these patients via the National Comprehensive Cancer Network Distress Thermometer (NCCN DT) instrument, as already collected in the DCI clinics per routine care.
- Describe the health care resource utilization (HCRU) at Duke Health for patients receiving BLENREP.

3. RESEARCH METHODOLOGY

3.1. Study Design

This is a single center retrospective observational study using electronic health record (EHR) data from routine cancer care practices at the DCI clinics. The study incorporates both cross-sectional and longitudinal components to yield novel insights regarding real-world use of BLENREP to treat RRMM and to describe the patient experience thereof. The study will analyze clinical data from adult patients with RRMM who were seen in the DCI outpatient oncology clinics on or after August 5, 2020. Demographic data, disease and treatment characteristics, data on comorbid conditions, and NCCN Distress Thermometer results will be manually abstracted from the medical record for each eligible patient using a standardized research electronic data capture (REDCap) case report form, to ensure data quality. Study feasibility was assessed in November 2021 via a preliminary medical record search. This search identified approximately 6000 patients with a corresponding ICD-9 or ICD-10 diagnosis code consistent with multiple myeloma who were seen in some capacity at Duke since January 2014. Approximately 30 of those patients also had a record of treatment with BLENREP between August 5, 2020, and Nov. 11, 2021. Note that BLENREP / Belantamab mafodotin – blmf received accelerated approval on August 5, 2020, by the Food and Drug Administration (FDA) for RRMM, and GSK (Glaxo SmithKline) requested withdrawal from the market on November 22, 2022.

Figure 1. Study Design Schema

3.2. Data Source / Data Collection

DCI's clinical EHR system will be used as the data source for chart abstractions into the REDCap case report forms.

3.2.1. DCI's EHR

The DCI EHR system, called Maestro Care, utilizes Epic (i.e., Epic Systems Corporation) healthcare software. Epic is a proprietary clinical database containing EHR data including medical diagnosis and procedures, prescriptions, laboratory results, provider notes, and practice-management data with longitudinal electronic patient data.

A particularly unique aspect of the data available within DCI standard care records is the inclusion of patient-reported outcomes (PRO) data. All patients seen in DCI clinics are asked to complete the NCCN Distress Thermometer instrument. This validated tool describes patients' experiences of illness, and contributors to their overall wellbeing (or lack thereof)¹. The NCCN DT also collects information regarding patients' physical symptoms, emotional or social difficulties, functional issues, and spiritual well-being. Our team has successfully used these data in other studies^{2,3,4}, which have yielded unexpected and important findings about the relationship between patient-reported distress and clinical outcomes.

3.2.2. Sources of Data

Maestro Care captures a comprehensive collection of clinical and operational information that providers reference at the time of an encounter. This includes all details of a patient's office visit, including but not limited to laboratory results, procedures, and diagnoses, as well as provider, pathology, radiology notes, detailed records of all biologics administrations and the results from the NCCN Distress Thermometer. Data pertaining to prescription medications includes Generic Product Identifier, generic and brand names, date of prescription start, strength, administration instructions, and reasons for discontinuation. Maestro Care also contains data pertaining to patient demographics (e.g., age, gender, ethnicity, insurance type and state).

3.2.3. Data Collection (Structured and Unstructured Data)

The study will utilize carefully developed methods to input manually abstracted chart data into explicitly structured data elements within a set of standardized case report forms that we design for each unique research project. The structured data elements are then actively managed within the REDCap data environment, ensuring data provenance, security, and completeness.

Maestro Care leverages structured data as well as extensive unstructured data to diagnose and develop patient care plans. The structured data, such as those described in section 3.2.2 are combined with unstructured data that are included in clinicians' notes and clinical reports. These notes may provide additional details relevant to the patient profile and symptoms that may lead to treatment differences and patterns. The notes can be used to provide pre-categorized information that may be codified into structured variables (such as severity of disease and rationale behind treatment changes, etc.). Text fields often include valuable information, regarding signs and symptoms, family history, disease-severity scores, medication changes, and physician rationale behind prescribing decision. Abstracted physicians' notes are key to identify patients in the RRMM cohort as well as their disease burden.

3.3. Study Population

3.3.1. Inclusion Criteria

To be included in the final study sample, patients must meet the following inclusion criteria provided below:

- Age \geq 18 years of age as of start of treatment with Belantamab mafodotin - blmf
- Patients with a corresponding ICD-9 or ICD-10 diagnosis code consistent with multiple myeloma seen at Duke.
- Patients with a record of starting treatment with Belantamab mafodotin - blmf for RRMM between August 5, 2020 and November 22, 2022.
- Patients having healthcare encounters at DCI \geq 1-month post index

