3.3.2. Exclusion Criteria

- Patients who were included in any clinical trial for BLENREP including expanded access clinical trials
- Age $>$ 89 years of age as of start of index therapy

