4. LIMITATIONS

The limitations of the study are primarily a function of the descriptive nature of the study objective; thus, lacking a control group by which to put the study results in context. However, given the nature of disease and treatments under consideration, the study may provide key insights into RRMM and belamaf use from a real-world, clinical practice setting.

The retrospective nature of this study also calls for caution in the interpretation of the study findings:

- This study may be affected by potential biases including reporting bias, selection bias, measurement error, and non-random missing data.
- Data are from locations/facilities within the DCI network only, so resources used outside of the network may be underestimated.
- Assessment of symptoms and treatment characteristics in real-world settings may be based on heterogeneous criteria and frequency, and the level of recording may vary across healthcare sites and providers.
- Comorbidities may be underestimated as they will be captured using ICD 9/10 diagnosis codes and diagnoses recorded in oncology clinical practices. Physicians may not include comorbidities that do not require active interventions or workups, and diagnoses made in primary care settings may not necessarily be captured.
- The study population includes RRMM patients which is heterogeneous in terms of disease severity, symptoms and treatments.
- Assessment of lab and clinical measures will be based on patients with data on the relevant tests or records. The results may not be representative of the full RRMM study population.
- The study population identified through this data set may not be generalizable to other populations in the US.
- The analyses are exploratory and descriptive in nature; no formal hypothesis-testing will be performed.

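### Eligibility does not require any BLENREP dose at DCI, so patients who started elsewhere and arrived later can enter with guaranteed survival to arrival and an incompletely captured early period

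*Combined protocol and SAP*

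**What the plan says.** Section 2.1 ties the study population to treatment at the centre. Its first objective is to "Describe the demographic and clinical characteristics of RRMM patients who receive BLENREP treatment at the DCI clinics", its third is to "Describe the clinical outcomes of RRMM patients who receive BLENREP treatment at the DCI clinics, as available", and the second refers back to the same patients.

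Apart from age, section 3.3.1 has three inclusion criteria:

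- Diagnosis: "Patients with a corresponding ICD-9 or ICD-10 diagnosis code consistent with multiple myeloma seen at Duke". The reference to Duke attaches to the myeloma code, not to BLENREP.
- Treatment: "Patients with a record of starting treatment with Belantamab mafodotin - blmf for RRMM between August 5, 2020 and November 22, 2022". No place of start or administration is given.
- Contact: "Patients having healthcare encounters at DCI \geq 1-month post index". This sets a minimum delay for an encounter. It sets no maximum, and it does not ask for contact at or before index.

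The exclusions in section 3.3.2 are age over 89 and "Patients who were included in any clinical trial for BLENREP including expanded access clinical trials". Treatment started outside DCI is not excluded.

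Index is not expressly defined. The age rules in sections 3.3.1 and 3.3.2 imply that it is the start of BLENREP. Section 3.6 plans Kaplan-Meier analysis of time to response, duration of response and OS, with no delayed entry or landmark. It summarises eye and HCRU events per patient per year without saying when a patient's time begins.

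**The concern.** The objectives describe people treated at DCI, while the criteria admit anyone with a suitable code, a recorded BLENREP start in the window and a later DCI encounter. Someone who began BLENREP at another practice and came to DCI some months afterwards qualifies. Two problems follow if time runs from the outside start.

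- **Survival.** The patient is in the data only because they lived long enough to reach DCI. Counting them at risk from the start adds time in which death was impossible and pushes the OS curve up.
- **Capture.** Dosing, delays, eye examinations, distress scores and admissions before arrival reach the DCI record only in part. If that time is in the denominator, eye and HCRU rates are pulled down and the dosing description is incomplete.

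This differs from the 1-month encounter rule, which imposes a death-free month on everyone. Dropping that rule would not remove the gap between an outside start and arrival. With about 30 patients, each one is about 3% of the cohort.

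**Working it through.** **The plan's own figure.** Section 3.5 finds about 30 treated patients, removes about 2 for trial or expanded-access participation and adds an unstated number of later starters. 30 − 2 = 28, which agrees with its expected cohort of up to about 30. There is no power calculation to reproduce. None of these counts separates DCI starters from outside starters.

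**Does an outside starter qualify?** Take an adult within the age limits, coded with myeloma at Duke, who started BLENREP elsewhere inside the window, was in no BLENREP trial and was first seen at DCI more than 1 month after starting. Every inclusion criterion is met and no exclusion applies, whether or not a dose was ever given at DCI.

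**Size of the survival bias.** The documents give no number of outside starters, no arrival delay and no OS figure, so all three are assumptions:

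- share started elsewhere, f = 10% to 30%
- months from start to DCI entry, d = 2 to 6
- true median OS, M = 6, 12 or 18 months, exponential, no censoring
- every patient survives 1 month, as a lower bound for the encounter rule

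Let S(t | T>a) = 2^(−(t−a)/M) for t ≥ a, and 1 before a. The naive curve is

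(1 − f) × S(t | T>1) + f × S(t | T>d).

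*Example: f = 0.20, d = 3, M = 12.*

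- True 6-month survival: 2^(−6/12) = 70.7%.
- With the 1-month rule alone: 2^(−5/12) = 74.9%.
- Outside starters: 2^(−3/12) = 84.1%.
- Naive: 0.8 × 0.7492 + 0.2 × 0.8409 = 76.8%.
- Added bias: 0.2 × (0.8409 − 0.7492) = 1.8 points (1.9 if the rounded percentages are subtracted).
- Effect of the 1-month rule itself: 74.9 − 70.7 = 4.2 points.
- Naive median: 12 + 12 × log2(0.8 × 2^(1/12) + 0.2 × 2^(3/12)) = 12 + 12 × log2(1.0854) = 13.4 months, against 13.0 with the 1-month rule alone. Added bias: 0.4 months.

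*Range over f and d:*

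| True median OS | 1-month rule alone | Naive median | Added bias (months) |
|---|---|---|---|
| 6 | 7.0 | 7.1 to 8.8 | 0.1 to 1.8 |
| 12 | 13.0 | 13.1 to 14.7 | 0.1 to 1.7 |
| 18 | 19.0 | 19.1 to 20.6 | 0.1 to 1.6 |

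With f = 0 the added bias is zero.

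**Per-year rates.** If a patient is followed F months from index and no event before arrival is captured, a constant true rate is multiplied by (F − d)/F. The cohort mean then falls by f × d/F. For an assumed F = 12 this runs from 0.1 × 2/12 = 1.7% to 0.3 × 6/12 = 15%. Partial capture from notes makes it smaller.

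**The case against.** The case for leaving the text alone has several parts.

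- **Context.** This is a single-centre study using the DCI record. Section 3.2.2 says that record holds biologics administrations, and sections 3.5 and 3.7 select the cohort by querying Duke's data. A recorded start may therefore usually be a start at Duke, and nothing in the documents shows that outside starters exist. That limits the likely number. It does not close the gap, because section 3.2.3 also uses clinicians' notes to identify the cohort, and a note can record an outside start.
- **Conflict with the objective.** A reader might infer that every outside starter contradicts section 2.1. That is not supported. A patient who began elsewhere and continued at DCI does receive BLENREP there. The conflict is strict only for those never dosed at DCI, although the early-period problem affects both groups.
- **Completeness.** A reader might also infer that nothing before arrival is recorded. Section 3.4.1 abstracts start and restart dates, dosing and reasons for delay, and notes may carry outside history. The period is better called incompletely captured. A patient already followed at DCI but infused elsewhere has no late first contact.
- **Disclosure.** Section 4 concedes "Data are from locations/facilities within the DCI network only, so resources used outside of the network may be underestimated", and lists selection bias and non-random missing data in general terms. The lowered eye and HCRU rates are therefore partly disclosed. Guaranteed survival to entry is not.
- **Size.** It is tempting to say that early mortality is understated in proportion to the share of outside starters, for example by 20%. That holds only until they arrive. In the example, 6-month mortality is understated by 1.8/25.1, about 7%. Sampling error is larger: with 30 patients and 75% survival, 1.96 × √(0.75 × 0.25/30) is about 15 points either side.
- **Deferral.** Sections 3.4 and 3.6 leave operational and analysis detail to a later SAP. Delayed entry could properly go there. Eligibility is settled in section 3.3.1 and could not.

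**Conclusion.** The concern holds in limited form. Section 3.3.1 does not carry through the condition in section 2.1 that BLENREP be received at DCI, and the planned Kaplan-Meier analysis has no provision for patients who arrive after starting elsewhere. If such patients are included and time runs from the outside start, OS is biased upward. Eye and HCRU rates are biased downward to the extent that outside events are missed.

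The size rests wholly on assumptions. In the worked example it is modest, less than half the effect of the separate 1-month rule on 6-month survival. Over the assumed range it is 0.1 to 1.8 months in median OS. With no outside starters it is nil, and the documents do not say whether there are any. The point is still worth settling, because the direction of bias is known and the charts are few enough to check.

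**What to change.** In section 3.3.1, require at least one BLENREP administration at a DCI clinic, confirmed from the EHR administration record. Define index explicitly as the first BLENREP dose, wherever given. This keeps patients who started elsewhere and continued at DCI, whom the objective covers, and removes those never dosed there.

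In section 3.6 or the SAP, for patients whose first DCI contact came after an outside start:

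- begin person-time for eye, HCRU and distress summaries at first DCI contact;
- enter them in the OS analysis at that date (delayed entry), or at the first DCI dose if that is later, since only then is the new criterion met;
- report how many there are and their delays, and show a sensitivity analysis limited to patients who started at DCI.

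Delayed entry assumes that time of arrival is unrelated to prognosis, which is why the sensitivity analysis is needed. The residual effect of the 1-month encounter rule is a separate matter that this change does not address.

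The cost is a phrase in the criterion, an index definition and a check of about 30 charts. A few patients may leave the cohort or be shown separately, and early risk sets will be slightly smaller.

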3.4.1. Patient Characteristics

The following patient characteristics will be measured as listed in the table below. Demographics will be summarized for the most recent measures on or prior to the index date, and all the other characteristics (i.e., clinical characteristics) will be abstracted at each clinic visit thereafter, until the end of follow-up. The end of follow-up will be defined as the date of the last clinical encounter available in the database prior to the IRB cut-off date.

Category	Variable	At Baseline	At Subsequent Clinical Encounters
Demographics	Age: Defined as of the index year.	x	
	Age groups: Patients will be assigned to one of the following age groups: 18-34, 35-44, 45-54, 55-64, 65-74, 75+.	x	
	Sex: Male, Female, Unknown	x	
	Weight	x	
	Height	x	
	Body mass index	x	

	Current Payer type: Whether the patient is covered by commercial, Medicaid, Medicare, self-insured, or was missing insurance payer type.	x	
	Race	x	
	RRMM diagnosed by DCI (yes/no)	x	
Comorbid Conditions	NCI Comorbidity Index	x	
Clinical Characteristics of RRMM	
 Subtype (e.g., IgA, IgG, light chain only, etc.) Cytogenetics Immunologic Studies Molecular testing results 	x	
Administered systemic treatments for MM prior to index	
 Medication Name Start/end dates of treatment Reason for discontinuation or change of treatment Line of therapy Prior HCST 	x	x
Treatment with BLENREP	
 Start/Re-start and end dates of treatment (as applicable) Dosing Line of therapy Reasons for discontinuation or delays of therapy 	x	x
NCCN Distress Thermometer	
 DT Score Problem List items 	x	x
Clinical Outcomes assessments	
 Myeloma markers (differs per patient and MM subtype; includes M-spike, UPEP, serum free light chains, etc.) Physician Reported Notes Disease response if available (using IMWG response criteria) Lab tests/assessments Death, if documented 		x
Ophthalmologic Status	
 Date of eye exam and results, as available. Documentation of ocular-toxicity 		x
HCRU	
 Disease-related hospitalizations Disease-related ED visits Disease-related outpatient visits 		x

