3.5. Feasibility Counts/Sample Size/Power Calculation

In order to determine the feasibility of conducting the study, a query of structured EMR data was conducted in November 2021. Since January 2014, approximately 6000 patients with a corresponding ICD-9 or ICD-10 diagnosis code consistent with multiple myeloma were seen in some capacity at Duke. Approximately 30 of those patients also had a record of treatment with Belantamab mafodotin - blmf for RRMM between August 5, 2020 and Nov. 11, 2021. For this study, we would exclude patients who were included in any clinical trial, including expanded access clinical trials (approximately 2 patients). Thus, our cohort would include up to approximately 30 patients (accounting for additional patients starting on BLENREP between the proposal date and the final IRB approval date).

As the intention of this study is to be descriptive in nature to provide insight into patient characteristics, treatment patterns, and dosing, no formal hypothesis/power calculations/sample size estimates are required.

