3.6. Data Analysis Considerations

Analyses will be undertaken by Duke University statisticians with expertise in patient-centered outcomes research. Details of the analyses will be furthered described in the statistical analysis plan (SAP) to be created at a later date.

Primary Objectives: Describe patient characteristics and treatment patterns for patients treated with BLENREP

Patient demographics and clinical characteristics (including diagnosis, laboratory measurements, general symptoms, and other comorbidities) will be summarized using descriptive statistics, consisting of the mean (\pm standard deviation [SD]) and median (with interquartile range [IQR]) values for continuous variables and frequency distributions and proportions for categorical variables.

Demographics will be described for the most recent measures on or prior to the index date. Clinical outcomes will be described until the end of follow-up. The end of follow-up will be defined as the date of the last clinical encounter available in the database prior to the IRB cut-off date. Summary statistics such as mean (\pm SD) and median (with IQR) values for continuous variables and frequency distributions and proportions for categorical variables will be calculated.

Time to clinical outcomes (i.e., time to response, duration of response, OS) will be analyzed using Kaplan-Meier analysis and median times to event will be reported (if the medians are achieved). 95% CIs will be reported in addition to the medians.

Treatment use and treatment patterns will be summarized using proportions (i.e., proportion of patients with select treatment for the control of symptoms). Sequences of treatment will also be described.

Secondary Objective: Describe Ophthalmology visit patterns and events

To the extent that they are available, events related to Ophthalmology outcomes (i.e., eye exams, outpatient visits, treatments for ocular toxicity, and other related HCRU events) will be summarized by the mean (\pm SD) and median (with IQR) number of events per patient per year and by the proportion and frequency distribution of patients with any occurrence of the respective

outcome. Treatment use and treatment patterns associated with ocular toxicity will be summarized using proportions (i.e., proportion of patients with select treatment for the control of symptoms).

Secondary Objective: Explore magnitude and sources of distress for these patients

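### Cohort entry requires a DCI encounter at least 1 month after index, so month-1 deaths and non-returners are left out and overall survival timed from BLENREP start reads too long

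*Combined protocol and SAP*

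**What the plan says.** Among the inclusion criteria, Section 3.3.1 lists "Patients having healthcare encounters at DCI \geq 1-month post index". No reason is given. Index is not formally defined, but the age exclusion in Section 3.3.2, "Age $>$ 89 years of age as of start of index therapy", ties it to the start of BLENREP.

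The third primary objective (Section 2.1) is to "Describe the clinical outcomes of RRMM patients who receive BLENREP treatment at the DCI clinics, as available". It sets no condition on survival or return.

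Section 3.6 states: "Time to clinical outcomes (i.e., time to response, duration of response, OS) will be analyzed using Kaplan-Meier analysis". Medians with 95% confidence intervals are to be reported. No time origin, landmark or delayed entry is given, and further detail is left to a later SAP. On follow-up, Section 3.4.1 says: "The end of follow-up will be defined as the date of the last clinical encounter available in the database", before the IRB cut-off.

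In the feasibility count (Section 3.5), the only deduction is for trial participants: "we would exclude patients who were included in any clinical trial, including expanded access clinical trials (approximately 2 patients". Nothing is taken off for the 1-month rule. Under Section 3.1, data are "manually abstracted from the medical record for each eligible patient". Section 4 lists selection bias among general limitations but does not mention this rule.

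**The concern.** The rule selects patients on what happens after treatment starts. To qualify, a patient must survive to 1 month and have a DCI encounter at or after that point. The criterion could also be read as requiring encounters that span at least 1 month. On either reading, nobody who dies in month 1 can enter. A patient who dies shortly after 1 month with no further encounter is lost as well.

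The analysed cohort is therefore not the one named in the primary objective. With OS timed from BLENREP start, every retained patient is guaranteed to survive to the first qualifying encounter, and each removed death raises every later point of the curve. Length of treatment and reasons for discontinuation, also primary, omit the same patients, as does response.

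The scope is limited. A patient who stops BLENREP early but is seen at DCI at or after 1 month stays in. Removing living patients who leave has an effect of unknown direction. The study is single-arm and descriptive, so what is at stake is the absolute survival figure and its denominator, not a treatment comparison.

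**Working it through.** **Plan's own count.** Section 3.5 gives about 30 treated patients less about 2 trial participants: 30 − 2 = 28. Allowing for later starters, this agrees with its figure of up to about 30. The number removed by the 1-month rule is not given. I use 28 starters below. This is an assumption, because the count stops at 11 November 2021 while the inclusion window runs to 22 November 2022.

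**Step 1: effect per excluded death, with no assumed survival distribution.** Suppose d of n starters die in month 1 and nobody is censored in that month. All-starter Kaplan-Meier survival at 1 month is then (n − d)/n, and the restricted curve equals the all-starter curve times n/(n − d) at every later time.

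| d | 28/(28 − d) | All-starter value behind a reported 70% |
|---|---|---|
| 1 | 1.037 | 70% × 27/28 = 67.5% |
| 2 | 1.077 | 70% × 26/28 = 65.0% |
| 3 | 1.120 | 70% × 25/28 = 62.5% |

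With 30 starters the last column becomes 67.7%, 65.3% and 63.0% (70% × 29/30, 28/30 and 27/30).

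**Step 2: how many deaths might be excluded.** The documents give no OS or early-death rate, so the true median m (in months) is assumed and varied.

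- Exponential: the share dead by 1 month is p = 1 − 2^(−1/m). Survival given alive at 1 month is S(t)/S(1), so the median reads m + 1.
- Weibull with shape 0.8 (higher early hazard): p = 1 − 2^(−a) with a = m^(−0.8), and the median reads m(1 + a)^1.25.

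| True median | Exponential p | Expected of 28 | P(at least one) = 1 − (1 − p)^28 | Median reads | Weibull p | Expected of 28 | Median reads |
|---|---|---|---|---|---|---|---|
| 6 | 10.9% | 3.1 | 96% | 7 | 15.2% | 4.3 | 7.8 |
| 9 | 7.4% | 2.1 | 88% | 10 | 11.3% | 3.2 | 11.0 |
| 12 | 5.6% | 1.6 | 80% | 13 | 9.1% | 2.5 | 14.1 |
| 15 | 4.5% | 1.3 | 73% | 16 | 7.6% | 2.1 | 17.2 |

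**Step 3: a second model.** Fix the month-1 death share q directly, with a constant hazard afterwards. For q from 2% to 15%, a true median of 6 months reads 6.15 to 7.53, and a true median of 12 reads 12.33 to 15.37.

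**Step 4: simulation at the planned size.** I took 28 starters, exponential survival with median 12 months, assumed uniform censoring from 6 to 30 months, and 6,000 runs. Restricting to 1-month survivors raised the Kaplan-Meier median by about 1 month on average. The shift is skewed: its median was about 0.2 month, and about 45% of runs showed no change. The restricted median was never below the all-starter median. The 95% sampling range of the all-starter median was about 6.9 to 22.7 months.

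**Step 5: source of the shift.** In a separate simulation (30 starters, exponential, no censoring), the mean sample median was 12.32 months for all starters, 13.33 for 1-month survivors timed from start, and 12.33 for the same survivors timed from month 1. With a true median of 6 the three values were 6.14, 7.16 and 6.16. The excess is the guaranteed first month.

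**The case against.** The OS claim is conditional. The plan states no origin and leaves detail to a later SAP. A SAP that started the clock at a landmark would not count the guaranteed time. That is correct, and the claim is worded accordingly. Such a SAP would, however, estimate survival among patients still in care, which is not the stated objective.

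The excluded charts remain in the EHR, so those patients can be recovered and counted at screening. This stands: the loss is not irreversible. But abstraction is planned for eligible patients only, and no count of exclusions under this rule is promised.

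The size rests on assumed inputs. This also stands. Even on the exponential inputs, the chance that no starter dies in month 1 is 4% to 27%. The 1-month shift is an average over a skewed distribution, and sampling error is larger. More starters than 28 would shrink the effect of each death.

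Dropping the rule recovers documented deaths only. Section 3.4.1 records death where documented, so an undocumented death outside the network would be censored. This limits the benefit without removing it.

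Finally, a minimum-contact rule is a recognisable choice for single-centre chart data, the outcomes objective is limited to what is available, and Section 4 names selection bias. But the objective's qualifier concerns data rather than eligibility, and the limitation names neither this rule nor its direction.

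**Conclusion.** The concern holds and should be fixed. The entry rule removes every month-1 death and every starter who does not return, so the cohort differs from the population in the primary objective. The direction for OS is certain for excluded deaths, provided OS is timed from BLENREP start; the plan leaves the origin open but points to that reading.

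The size cannot be taken from the documents. Each excluded death among 28 starters lowers the all-starter value behind a reported 70% by 2.5 percentage points. Across the assumed exponential and Weibull scenarios the median reads about 1 to 2.2 months too long. With month-1 mortality of 2% to 15% set directly, the excess is about 0.2 to 1.5 months for a true median of 6 and 0.3 to 3.4 months for a true median of 12. If no starter died in month 1, that part of the bias is nil, but only a reported exclusion count would show it. Sampling error is larger; the planned confidence interval would not reveal the bias.

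**What to change.** 1. Define index and the OS origin as the date of the first BLENREP dose.
2. Drop the 1-month criterion for cohort entry and for the OS, response and treatment-pattern analyses. Include all starters who meet the other criteria, and censor the living at the last encounter, already the defined end of follow-up.
3. Keep a minimum follow-up only for annualised utilisation or distress summaries, if wanted.
4. Report how many starters had under 1 month of follow-up and why (death or loss), and note that undocumented deaths outside the network will be missed.

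If the rule is kept, let each patient enter the OS risk set at the first qualifying encounter rather than at index, label the result as survival given alive and in care at that point, and report the number excluded with reasons.

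The cost is a few lines of protocol or SAP text and a few extra charts: about 1 to 4 early deaths among 28 under the assumptions above, plus any early leavers. Reported OS may look slightly less favourable, and annualised rates will need a rule for very short follow-up. The change is easiest before abstraction.
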